- Change from baseline to each scheduled assessment in the number of days of opioid analgesic use for EAP during the previous 4-week period as assessed in the eDiary
- Change from baseline to each scheduled assessment in the number of pelvic pain-free days (assessed on the VRS) during the previous 4-week period
- Change from baseline to each scheduled assessment in ability to perform daily activities during the previous 4-week period, as assessed in the eDiary (daily function NRS)
- Change from baseline to each scheduled assessment in the number of days with no difficulty in doing daily activities due to EAP during the previous 4-week period as assessed in the eDiary (daily function NRS)
- Change from baseline to each scheduled assessment in the number of days when dyspareunia was a problem during the previous 4-week period (including days when sexual intercourse was avoided because of anticipation of pain) as assessed on the dyspareunia VRS

- Change from baseline to each scheduled assessment in the number of days when sexual intercourse was avoided because of anticipation of pain during the previous 4-week period as assessed on the dyspareunia VRS
- Change from baseline to each scheduled assessment in the number of days with uterine bleeding (including spotting) during the previous 4-week period measured by eDiary
- Change from baseline to each scheduled assessment in the number of days when school or work was missed due to EAP in the previous 4-week period as reported in the eDiary
- Change from baseline to each scheduled assessment in the number of days when the subject had to go to bed or lie down due to EAP in the previous 4-week period as reported in the eDiary
- Change from baseline to each scheduled assessment in the Pain, Control and powerlessness, Emotional well-being, Social support, Self-image dimensions and the Modular sexual relationship questionnaire of EHP-30 scores
- Change from baseline to each scheduled assessment in the Health Related Productivity Questionnaire (HRPQ) scores
- Number of non-study endometriosis related health visits, number of days in hospital and type of procedures performed based on Health Resource Utilization Questionnaire (HRUQ) at each scheduled assessment
- Change from baseline to each scheduled assessment in the Physician/Subject Surgery Intention Question (PSIQ/SSIQ)
- Change from baseline to each scheduled assessment in the PROMIS Fatigue – Short Form 6a

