4.2.8. Missing, Unused, and Spurious Data

4.2.8.1. Efficacy Endpoints Missing Data

Summary statistics will be based primarily on non-missing values. The planned statistical analyses aim to estimate the efficacy of linzagolix versus placebo while under randomized treatment and therefore lack of data after treatment discontinuation will not be considered as missing for these analyses.

Subjects who cannot be assessed as responders for the co-primary efficacy endpoints, e.g. due to lack of on treatment pain data (i.e. subjects who received less than 28 days of treatment), will be considered as non-responders. In addition, for endpoints assessing the numeric change from baseline, such subjects will be assigned a change from baseline of zero. It is expected that very few subjects will be affected by these rules.

There may be missing data during the screening period and whilst under treatment, for example, missed days of completing the eDiary. The primary analyses will use observed data only in such cases provided that a minimum number of completed daily eDiary entries are available. This effectively assumes that the individual values such as daily eDiary assessments (observed or not) are independent of being missing.

Further details on the handling of missing values and the methods and planned sensitivity analyses to check the robustness of the analysis results under alternative assumptions with regards to missing data are provided in the analyses sections. As additional analyses, in order to estimate the effect of treatment policy, a reference based multiple imputation approach will be used for the co-primary endpoints for subjects who discontinue the study early under the assumption that the efficacy of the linzagolix treated subjects gradually transitions to that observed in the placebo subjects.

Missingness Assumptions:

Missing At Random (MAR): Missingness is independent of unobserved outcomes given observed data. Subjects with missing data can be modeled based on similar subjects with available data if we account in the model for relevant observed factors.

Missing Not At Random (MNAR): The probability of missingness depends on the unobserved outcome and cannot be predicted only based on observed data.

Multiple Imputation Methodology:

Multiple imputation inference involves three distinct steps:

Sponsor:	ObsEva		
Protocol:	18-OBE2109-00	18-OBE2109-003	
Document Version No.:	V5.0		

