4.6.4. Additional Secondary Endpoints

All additional efficacy endpoints will be summarized by descriptive statistics for each treatment group, for each time point, including summaries of change from baseline when applicable. Individual linzagolix versus placebo treatment group comparisons will be made.

In general, between group comparisons for continuous endpoints will be analyzed via analysis of (co)variance. Between-group comparisons for binary endpoints will be analyzed via logistic regression. Between-group comparisons for ordinal categorical data will be analyzed using a Mantel-Haenszel test, or using Koch's method when there is also a baseline covariate.

As described in section 4.2.5 additional secondary endpoints will use Bonferroni correction for p-values of comparison of treatment groups at each visit. The analyses do not form part of the fixed-sequence strategy being used for the ranked secondary endpoints and will not be fully controlled for an overall type I error rate.

Values for all endpoints that are collected daily using the eDiary (from Section 4.6.4.1 to Section 4.6.4.18) will be based on the 28 calendar days immediately prior to and including the day of the corresponding visit or prior to and including the last treatment administration date for Month 6, or the 28 calendar days immediately prior to and including the last dose date for subjects who discontinue treatment prior to the visit in question (or fewer if treatment is stopped less than 4 weeks after first dose date), in order to estimate the treatment effect while under treatment. The last 28 days on treatment will be used at all subsequent scheduled visits for those discontinued subjects. Descriptive summaries for each 28-day period will be performed in two ways however:

- Once including only values of 28 days prior to Month X, i.e. using the last 28 days prior to Month X eCRF visit date for subjects who have not discontinued up to that month. If subjects discontinued prior to Month X the corresponding value will be missing from the summary at Month X;
- Once applying the while on treatment strategy, i.e. using the last 28 days prior to Month X eCRF visit date for subjects who have not discontinued up to that month, and for subjects who discontinued prior to Month X, the last 28 days prior to treatment discontinuation will be used. For all subsequent timepoints (Month X+1, etc.) the same last 28 days prior to treatment discontinuation will be used.

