Corresponding baseline values will be calculated based on the two baseline menstrual cycles, which may not be exactly 28 days each.

The values for other endpoints (monthly and 3-monthly questionnaires from Section 4.6.4.19 to Section 4.6.4.26) are defined as the value at the corresponding visit or value falling into the corresponding visit window as described in section 4.2.9. For these other endpoints, descriptive summaries by visit will be

Sponsor:	ObsEva		
Protocol:	18-OBE2109-00	3	
Document Version No.:	V5.0	Document Date:	13-JUN-2022

performed in two ways, once including values at the corresponding visit or value falling into the corresponding visit window as described in section 4.2.9, and once applying the while on treatment strategy, i.e., including values from the discontinued visits at each next scheduled visit.

For endpoints based on daily diary data, analyses will use observed data only in such cases, provided that a minimum number of 43% (at least 12 days of each 28-day period) completed daily eDiary entries are available.

4.6.4.1. Clinically meaningful reduction at scheduled visits other than Month 3 for DYS and NMPP

The proportion of responders for DYS and NMPP based on daily e-diary data will be reported at each visit (each 28 days period) along with odds-ratio and 97.5% confidence intervals from logistic regression as described in Section 4.6.2.1.2.

The same responder definition defined for primary endpoint in Section 4.6.2.1.1 will be used, but for other scheduled visits.

Due to the war situation in Ukraine, data from subjects in Ukraine sites may be incomplete, missing or uncleaned. The descriptive analysis of proportion of responders for DYS and NMPP at each visit will be repeated, excluding data collected after 24FEB2022 for subjects from Ukraine sites, for the Follow-up period only (Follow-up set), as the main treatment period was completed before the start of the war. Listings will contain country information to identify those subjects.

4.6.4.2. Change from baseline to each scheduled assessment in mean pelvic pain scores for DYS, NMPP and overall pelvic pain, during the previous 4-week period assessed on the NRS and VRS

The change from baseline to each scheduled assessment in mean pelvic pain scores for DYS, NMPP and overall pelvic pain will be analyzed as described for the ranked secondary endpoint in Section 4.6.3.1 (continuous summary and analysis of covariance at each visit).

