4.6.4.3. Change from baseline to each scheduled assessment in the number of days with moderate to severe pelvic pain during the previous 4-week period assessed on the VRS

The actual value and change from baseline of number of days with moderate or severe pelvic pain collected in the e-diary on the VRS will be summarized for each 28-day period. The baseline value will be computed by averaging the number of days with moderate or severe pelvic pain of the two baseline menstrual cycles. The number of days will be analyzed with a negative binomial model including baseline

Sponsor:	ObsEva		
Protocol:	18-OBE2109-003		
Document Version No.:	V5.0	Document Date:	13-JUN-2022

as a covariate. The estimated least square means treatment differences along with 97.5% CI will be provided.

SAS Code for negative binomial model with repeated measurements

```
proc genmod data=dataset order=internal ;
    class treatment;
    model nbdays = baseline treatment / dist=negbin type3 ;
    lsmeans treatment / diff = control('1') exp at means cl alpha=0.05
adjust=bon;
estimate 'TRT Placebo' intercept 1 base %sysevalf(&meanbase.) trt01pn 1 0 0 /
exp E;
estimate 'TRT LGX 75' intercept 1 base %sysevalf(&meanbase.) trt01pn 0 1 0 /
exp E;
estimate 'TRT LGX 200' intercept 1 base %sysevalf(&meanbase.) trt01pn 0 1 0 /
exp E;
estimate 'TRT LGX 200' intercept 1 base %sysevalf(&meanbase.) trt01pn 0 1 0 /
exp E;
estimate 'TRT LGX 200' intercept 1 base %sysevalf(&meanbase.) trt01pn 0 0 1
/ exp E;
    ods output lsmeans=lsm diffs=lsmd Estimates=estimate ;
```

run;

"meanbase" macro variable is the mean value of baseline over the same selection of subjects used in the model

4.6.4.4. Change from baseline to each scheduled assessment in the mean worst pelvic pain score defined as the mean of the 5 highest daily pain scores reported during the previous 4-week period assessed on the NRS

The actual value and change from baseline of the mean worst pelvic pain score, defined as the mean of the 5 highest daily pain scores reported during each 28-day period will be summarized for each 28-day period. The baseline mean worst pelvic pain score will be the average of the mean pelvic pain score of each of the two baseline menstrual cycles. An analysis of covariance will be performed for each period.

If less than 5 days of pain score data is available, the mean worst pelvic pain will be defined as the mean of the available daily pain scores.

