4.6.4.8. Change from baseline to each scheduled assessment in opioid analgesic use for EAP as reported in the eDiary during the previous 4-week period based on morphine milligram

Sponsor:	ObsEva		
Protocol:	18-OBE2109-003		
Document Version No.:	V5.0	Document Date:	13-JUN-2022

equivalent (MME)

Opioid analgesic use for EAP will also be assessed based on morphine milligram equivalent (MME). The mean daily amount for each 28-day period reported in eDiary as pill count will be converted in MME.

No opioids are allowed in Ukraine. Subjects from Ukraine will therefore be excluded from the analysis in MME. If some opioids are nevertheless recorded for subjects from Ukraine, they will not be considered, as the conversion in MME would be unknown. Those opioids records will however be considered for other analgesic use analyses not requiring conversion in MME.

Due to a low number of subjects using any opioids, opioids use will not be analyzed, only a listing with by subject mean daily opioid use in MME will be provided.

4.6.4.9. Change from baseline to each scheduled assessment in the number of days of analgesic use (including any class) for EAP during the previous 4-week period as assessed in the eDiary

The actual value and change from baseline in the number of days with analgesic use for EAP collected in the e-diary will be summarized for each 28-day period. The number of days will be analyzed using a negative binomial model, including baseline as a covariate The estimated least square means treatment differences along with 97.5% CI will be provided. The baseline value will be computed by averaging the number of days with analgesic use of the two baseline menstrual cycles.

4.6.4.10. Change from baseline to each scheduled assessment in the number of days of opioid analgesic use for EAP during the previous 4-week period as assessed in the eDiary

The actual value and change from baseline in the number of days with opioid analgesic use for EAP collected in the e-diary will be calculated for each 28-day period. The baseline value will be computed by averaging the number of days with opioid analgesic use of the two baseline menstrual cycles.

Due to a low number of subjects using any opioids, number of days with opioid analgesic use will not be analyzed, only a by subject listing will be provided.

4.6.4.11. Change from baseline to each scheduled assessment in the number of pelvic pain-free days

CRS-BS-TP-000005 V 1.0

Sponsor:	ObsEva			

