Protocol:	18-OBE2109-00	18-OBE2109-003		
Document Version No.:	V5.0	Document Date:	13-JUN-2022	

(assessed on the VRS) during the previous 4-week period

The actual value and change from baseline of number of pelvic pain-free days collected in the e-diary will be summarized for each 28-day period. The number of days will be analyzed with a negative binomial model, including baseline as a covariate. The estimated least square means treatment differences along with 97.5% CI will be provided. The baseline value will be computed by averaging the number of pelvic pain-free days of the two baseline menstrual cycles.

4.6.4.12. Change from baseline to each scheduled assessment in ability to perform daily activities during the previous 4-week period, as assessed in the eDiary (daily function NRS)

Daily activities score for each subject will be calculated by averaging over the corresponding 28 calendar days immediately prior to and including the day each visit (or the 28 calendar days immediately prior to and including the last dose date for subjects who discontinue treatment prior to Month 6). The baseline mean of daily activities score will be calculated by averaging over the two baseline menstrual cycles. The actual value and change from baseline of daily activities score will be each activities score will be each activities score will be calculated. The score will be summarized as a continuous variable and change from baseline for each 28-day period will be evaluated using analysis of covariance.

4.6.4.13. Change from baseline to each scheduled assessment in the number of days with no difficulty in doing daily activities due to EAP during the previous 4-week period as assessed in the eDiary (daily function NRS)

The actual value and change from baseline of number of days with no difficulty in doing daily activities due to EAP collected in the e-diary will be summarized for each 28-day period. The number of days will be analyzed with a negative binomial model, including baseline as a covariate. The estimated least square means treatment differences along with 97.5% CI will be provided. The baseline value will be computed by averaging the number of days of the two baseline menstrual cycles.

4.6.4.14. Change from baseline to each scheduled assessment in the number of days when dyspareunia was a problem during the previous 4-week period (including days when sexual intercourse was avoided because of anticipation of pain) as assessed on the dyspareunia VRS

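### Nine diary day-count endpoints are modelled as raw counts with no offset for answered diary days, so an unrecorded day acts as a day without the event; separately, the HRUQ negative binomial is written on a change score

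*SAP*

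**What the plan says.** The only model code for day counts is in SAP 4.6.4.3: "model nbdays = baseline treatment / dist=negbin type3". Its terms are baseline and treatment, with no offset. Sections 4.6.4.9, .11, .13, .14, .15, .16, .17 and .18 prescribe the same analysis; in 4.6.4.11, for example, "The number of days will be analyzed with a negative binomial model, including baseline as a covariate". No section rescales the modelled count to 28 days or gives the model an answered-days denominator. Opioid days (4.6.4.10) are outside the point: "number of days with opioid analgesic use will not be analyzed, only a by subject listing will be provided".

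Section 4.6.4 admits diary data "provided that a minimum number of 43% (at least 12 days of each 28-day period) completed daily eDiary entries are available". It also allows a shorter window, "or fewer if treatment is stopped less than 4 weeks after first dose date", and reuses that window at every later visit. Section 4.2.8.1 may instead apply to women treated for under 28 days: "such subjects will be assigned a change from baseline of zero".

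For error control, section 4.6.4 says these analyses "will not be fully controlled for an overall type I error rate".

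Section 4.6.4.21 applies a negative binomial, with baseline as covariate, to the change from baseline in HRUQ health visits and hospital nights.

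**The concern.** Using observed days only is sound for a mean. For a count it is not: a day with no diary entry adds zero, exactly as an event-free day does. The SAP does not say this in words, but it follows from counting event days with no denominator. It remains true even under the SAP's own assumption that a daily value is independent of whether it is missing.

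The SAP accepts the principle elsewhere. Its V3.0 change log moved pill counts from totals to daily means because a mean allows for unrecorded days. The nine day counts were left unscaled in their models.

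The stake is an artefact in the treatment comparison. The arm with poorer completion looks better on unfavourable days (pain, bleeding, missed work) and worse on pain-free and no-difficulty days. Mean pain, mean pill count and mean daily function already adjust for missing days. Bleeding days and missed-work days have no diary-based version that does.

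The HRUQ issue is separate. A negative binomial response must be a non-negative count, and a change score need not be.

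**Working it through.** **The plan's own figure.** 12/28 = 42.9%, which rounds to the stated 43%. Up to 28 − 12 = 16 days may be unrecorded.

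**Level of the count.** Expected raw count = true 28-day count × answered days/28.
- True 10 days, 24 answered: 10 × 24/28 = 8.6.
- True 10 days, 12 answered: 10 × 12/28 = 4.3, a shortfall of 57%.

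**Treatment ratio.** Raw ratio = true ratio × (answered days in one arm / answered days in the other). For 80% against 90%, a true 1.00 becomes 0.80/0.90 = 0.89 and a true 0.70 becomes 0.62. In the opposite direction, 1.00 becomes 1.125 and 0.70 becomes 0.79.

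**Baseline.** Protocol inclusion criterion 8 allows two cycles totalling 42 to 76 days, so the mean cycle is 21 to 38 days, or 0.75 to 1.36 times the 28-day window. Baseline counts are not scaled either.

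**False positives.** From the documents: 150 per arm, three arms, two-sided 0.025 per comparison, 12-day floor. Assumed: daily event probability Beta across women (a+b = 4); baseline of two cycles of 21 to 38 days at 90% completion; completion varying between women (Beta, precision 12). There is no true effect. The raw model uses the count baseline and no offset. In the full-link rows each woman has the same daily probability at baseline and on treatment (1000 trials per scenario); in the 0.5 rows the correlation is 0.5 (600 trials). The Monte Carlo standard error is about 0.5 to 0.6 points near 2.5%.

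| Completion | Mean answered days | Ratio | Baseline link | p = 0.05 | 0.10 | 0.25 | 0.50 |
|---|---|---|---|---|---|---|---|
| 90 vs 90% | 25.2 vs 25.2 | 1.00 | full | 2.7% | 3.5% | 2.4% | 2.0% |
| 90 vs 88% | 25.2 vs 24.7 | 0.98 | full | 3.5% | 3.3% | 3.1% | 4.0% |
| 90 vs 86% | 25.2 vs 24.1 | 0.96 | full | 2.9% | 2.4% | 4.8% | 12.7% |
| 90 vs 85% | 25.2 vs 23.8 | 0.94 | full | 3.2% | 3.7% | 8.0% | 22.1% |
| 90 vs 80% | 25.2 vs 22.5 | 0.89 | full | 3.9% | 8.6% | 31.2% | 74.6% |
| 90 vs 85% | 25.2 vs 23.8 | 0.94 | 0.5 | 5.0% | 4.0% | 3.7% | 8.7% |
| 90 vs 80% | 25.2 vs 22.5 | 0.89 | 0.5 | 4.7% | 6.7% | 14.2% | 42.8% |

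The Ratio column is lower-arm over higher-arm answered days, for example 22.5/25.2 = 0.89. A separate run of the 86% case gave 6.9% and 15.7% at 0.25 and 0.50, so the entries are approximate. At equal 90% completion the mean raw counts were 1.26, 2.53, 6.3 and 12.6 against true values of 1.4, 2.8, 7.0 and 14.0.

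**With offset log(answered days) and baseline per 28 answered days.** Over all 32 scenarios the ratio was 0.98 to 1.01 and false positives were 0.3% to 4.0%. At probability 0.50 with the full baseline link, the dispersion went to zero in every fit and the test was conservative (0.3% to 1.2%). A beta-binomial on event days out of answered days gave 1.5% to 3.3% in eight scenarios (400 trials each).

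**Independent check.** With daily probability 0.4 and no baseline covariate (600 trials), 90% against 80% gave 28.5% false positives without the offset and 3.0% with it. Equal 85% completion gave 1.3% and 1.2%.

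**Short windows alone.** If 5% (10%) of one arm and none of the other stop on days 14 to 27, the ratio is 0.988 (0.976).

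**HRUQ.** A woman going from 2 visits to 0 has a change of 0 − 2 = −2, outside the negative binomial's range.

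**The case against.** - **Bias needs unequal completion, and the documents show none.** This is correct, and every completion rate above is assumed. The 75% diary requirement at screening, the daily alarm and missed-entry alerts, the compliance checks at visits and the blinding all make a large gap less likely. They do not rule it out, and equal completion still leaves the estimated days too low.
- **The largest percentages depend on the set-up.** The 74.6% needs a common event and a fully correlated baseline; correlation 0.5 gives 42.8%. For rare events, or gaps of a few points, inflation is small. The multiplication of the ratio does not depend on these settings.
- **Some adjustment is already planned.** Section 4.6.4.15 subtracts missing days from a denominator, but only in a descriptive proportion. Next-day back-fill recovers some missed days in 4.6.4.9. The HRPQ analyses work absenteeism, but by one-week recall. None of these corrects the nine models.
- **The offset model is not perfect.** It was conservative for very common events, hence the beta-binomial fallback.
- **The consequence is limited.** These endpoints lie outside the fixed sequence, and opposite effects on favourable and unfavourable days may help expose an artefact. This stands and limits the severity.
- **The HRUQ sentence is probably a wording slip.** This is likely, since 4.6.4.3 also has a change title but models the count. It still needs correcting.

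**Conclusion.** The concern holds. Nine models omit the denominator that the 12-day rule makes necessary. The level of the estimated day counts is understated in proportion to missing days, by about 10% at 90% completion. The treatment ratio is distorted only if completion or window length differs by arm; it is then multiplied by the ratio of answered days (0.94 for 85% against 90%, 0.89 for 80% against 90%). False-positive inflation is material for common events and small for rare ones. Completion by arm, event rates and stopping rates are assumptions. Severity is minor to moderate: the change should be made, but no co-primary or ranked conclusion depends on it. Confidence is high that the denominator is missing; the size of any actual bias is unknown. The HRUQ wording is wrong as written and is probably a slip.

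**What to change.** Add an offset of log(days with a non-missing answer to that item) to the nine models, and apply the 12-day minimum to those answered days. In 4.6.4.9, count back-filled days as answered. Report adjusted means per 28 days, put baseline and descriptive summaries on the same scale, and tabulate answered days by arm and visit.

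In 4.6.4.14 and .15, treat a recorded answer of no sexual activity for reasons unrelated to endometriosis as an observed non-event day. The protocol endpoint, the "number of days when sexual intercourse was avoided because of anticipation of pain during the previous 4-week period", then remains a number of days; a rate among sexually relevant days can be supplementary only.

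Because counts are capped at 28, state that a beta-binomial model of event days out of answered days is used if the negative binomial fails to converge or its dispersion goes to zero.

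If Month 6 data are already unblinded, keep the planned model and add this as a labelled sensitivity analysis. That is probably the case: the Month 6 thresholds entered the SAP at V4.0, and section 4.3 allows results to be released to the sponsor after that update.

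In 4.6.4.21, name the counts of visits and nights as the response, with baseline as covariate.

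The cost is one derived variable and one model option (or one sensitivity output) per endpoint, plus one sentence for the HRUQ. No new data are needed. The offset does not correct missingness that depends on that day's pain.
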